5.11. Association of Immunogenicity with Exposure and Safety

5.11.1. Immunogenicity and Exposure Data

Potential association between immunogenicity variables and systemic exposure to casirivimab and imdevimab may be explored by treatment groups. Plots of individual casirivimab and imdevimab concentration time profiles may be provided to examine the potential impact of ADA category and maximum titer category and NAb status on these profiles.

5.11.2. Immunogenicity and Safety

Potential association between immunogenicity variables and safety may be explored with a primary focus on the following safety events during the on-treatment period:

- Injection site reaction (serious or severe and lasting 24 hours or longer)
- Hypersensitivity (SMQ: Hypersensitivity [Narrow])

6. DATA CONVENTIONS

The following analysis conventions will be used in the statistical analysis.

6.1. Definition of Baseline for Efficacy/Safety Variables

Unless otherwise specified, the Baseline assessment for all measurements will be the latest available valid measurement taken prior to the administration of study drug.

6.2. Data Handling Convention for Efficacy Variables

Not applicable as clinical efficacy variables are not collected within this study.

6.3. Data Handling Convention for Missing Data

Missing data will not be imputed in listings. This section includes the methods for missing data imputation for some summary analyses, if necessary.

For categorical variables, participants with missing data are not included in calculations of percentages unless otherwise specified. When relevant, the number of participants with missing data is presented.

Adverse event

If the severity of a TEAE is missing, it will be classified as “severe” or “Grade 3” in the frequency tables by intensity of TEAEs. If the assessment of relationship of a TEAE to the investigational product is missing, it will be classified as related to the investigational product.

Medication/Procedure

If a medication date or time is missing or partially missing and it cannot be determined whether it was taken prior or concomitantly or stopped prior to the first study treatment administration, it will be considered as concomitant medication/procedure by imputing the start date on the date of first study treatment administration.

Potentially Clinically Significant Value (PCSV)

For PCSVs with 2 conditions, one based on a change from baseline value and the other on a threshold value or a normal range, with the first condition being missing, the PCSV will be based only on the second condition.

For a PCSV defined on a threshold and/or a normal range, this PCSV will be derived using this threshold if the normal range is missing; e.g., for eosinophils the PCSV is >0.5 giga/L or $>\text{ULN}$ if $\text{ULN} \geq 0.5$ giga/L. When ULN is missing, the value 0.5 should be used.

Measurements flagged as invalid by the laboratory will not be summarized or taken into account in the computation of PCSVs.

6.4. Out of window visits

Analysis will be based on nominal visits; analysis windows will not be defined.

6.5. Unscheduled Assessments

Extra assessments (e.g. laboratory data or vital signs associated with non-protocol clinical visits or obtained in the course of investigating or managing AEs) will be included in listings and PCSV summaries. For by visit summaries, only scheduled visit values will be included. Both scheduled and unscheduled measurements will be considered for determining abnormal values from laboratory data, vital sign, as well as the baseline values.

6.6. Pooling of Centers for Statistical Analyses

No plan of pooling of centers for analysis.

7. INTERIM ANALYSIS

No interim analysis is planned.

8. SOFTWARE

All analyses will be done using SAS Version 9.4 or higher.

10. APPENDIX

10.1. Criteria for Potentially Clinically Significant Values (PCSV)

If baseline is missing, only post-baseline criteria will be considered.

Parameter	PCSV	Comments
Clinical chemistry		
ALT	>3 and \leq 5 ULN and baseline \leq 3 ULN >5 and \leq 10 ULN and baseline \leq 5 ULN >10 and \leq 20 ULN and baseline \leq 10 ULN >20 ULN and baseline \leq 20 ULN	Enzymes activities must be expressed in ULN, not in IU/L. Each category is calculated independently.
AST	>3 and \leq 5 ULN and baseline \leq 3 ULN >5 and \leq 10 ULN and baseline \leq 5 ULN >10 and \leq 20 ULN and baseline \leq 10 ULN >20 ULN and baseline \leq 20 ULN	Enzymes activities must be expressed in ULN, not in IU/L. Each category is calculated independently.
Alkaline Phosphatase	>1.5 ULN and baseline \leq 1.5 ULN	Enzymes activities must be expressed in ULN, not in IU/L.
Total Bilirubin	>1.5 and \leq 2 ULN and baseline \leq 1.5 ULN >2 ULN and baseline \leq 2.0 ULN	Must be expressed in ULN, not in μ mol/L or mg/L.
Conjugated bilirubin	>35% Total Bilirubin and TBILI >1.5 ULN, and baseline Total Bilirubin \leq 35% or TBILI \leq 1.5 ULN	Conjugated bilirubin dosed on a case-by-case basis
ALT and Total Bilirubin	ALT > 3 ULN and TBILI > 2 ULN, and baseline ALT \leq 3 ULN or TBILI \leq 2 ULN	

Parameter	PCSV	Comments
CPK	>3 and \leq 10 ULN and baseline \leq 3ULN >10 ULN and baseline \leq 10ULN	
Creatinine	\geq 150 μ mol/L (Adults) or \geq ULN (if ULN \geq 150 μ mol/L) and baseline $<$ 150 μ mol/L or $<$ ULN (if ULN \geq 150 μ mol/L) \geq 30% change from baseline \geq 100% change from baseline	3 independent criteria
Creatinine Clearance (Cockcroft's formula)	<15 ml/min and baseline \geq 15 ml/min (end stage renal impairment) \geq 15 to <30 ml/min and baseline \geq 30 ml/min (severe renal impairment) \geq 30 to < 60 ml/min and baseline \geq 60 ml/min (moderate renal impairment) \geq 60 to < 90 ml/min and baseline \geq 90 ml/min (mild renal impairment)	Four independent criteria
Uric Acid		Two independent criteria
Hyperuricemia:	>408 μ mol/L or >ULN (if ULN \geq 408 μ mol/L) and baseline \leq 408 μ mol/L or \leq ULN (if ULN \geq 408 μ mol/L)	
Hypouricemia:	<120 μ mol/L or <LLN (if LLN \leq 120 μ mol/L) and baseline \geq 120 μ mol/L or \geq LLN (if LLN \leq 120 μ mol/L)	
Blood Urea Nitrogen	\geq 17 mmol/L or \geq ULN (if ULN \geq 17 mmol/L) and baseline <17 mmol/L or <ULN (if ULN \geq 17 mmol/L)	Two independent criteria
Chloride		Two independent criteria
Hypochloremia:	<80 mmol/L or <LLN (if LLN \leq 80 mmol/L) and baseline \geq 80 mmol/L or \geq LLN (if LLN \leq 80 mmol/L)	
Hyperchloremia:	>115 mmol/L or >ULN (if ULN \geq 115 mmol/L) and baseline \leq 115 mmol/L or \leq ULN (if ULN \geq 115 mmol/L)	

Parameter	PCSV	Comments
Sodium Hyponatremia: Hypernatremia:	$\leq 129 \text{ mmol/L}$ or $\leq \text{LLN}$ (if $\text{LLN} \leq 129 \text{ mmol/L}$) and baseline $> 129 \text{ mmol/L}$ or $> \text{LLN}$ (if $\text{LLN} \leq 129 \text{ mmol/L}$) $\geq 160 \text{ mmol/L}$ or $\geq \text{ULN}$ (if $\text{ULN} \geq 160 \text{ mmol/L}$) and baseline $< 160 \text{ mmol/L}$ or $< \text{ULN}$ (if $\text{ULN} \geq 160 \text{ mmol/L}$)	Two independent criteria
Potassium Hypokalemia Hyperkalemia	$< 3 \text{ mmol/L}$ or $< \text{LLN}$ (if $\text{LLN} \leq 3 \text{ mmol/L}$) and baseline $\geq 3 \text{ mmol/L}$ or $\geq \text{LLN}$ (if $\text{LLN} \leq 3 \text{ mmol/L}$) $\geq 5.5 \text{ mmol/L}$ or $\geq \text{ULN}$ (if $\text{ULN} \geq 5.5 \text{ mmol/L}$) and baseline $< 5.5 \text{ mmol/L}$ or $< \text{ULN}$ (if $\text{ULN} \geq 5.5 \text{ mmol/L}$)	Two independent criteria
Total Cholesterol	$\geq 7.74 \text{ mmol/L}$ or $\geq \text{ULN}$ (if $\text{ULN} \geq 7.74 \text{ mmol/L}$) and baseline $< 7.74 \text{ mmol/L}$ or $< \text{ULN}$ (if $\text{ULN} \geq 7.74 \text{ mmol/L}$)	Threshold for therapeutic intervention.
Triglycerides	$\geq 4.6 \text{ mmol/L}$ or $\geq \text{ULN}$ (if $\text{ULN} \geq 4.6 \text{ mmol/L}$) and baseline $< 4.6 \text{ mmol/L}$ or $< \text{ULN}$ (if $\text{ULN} \geq 4.6 \text{ mmol/L}$)	Threshold for therapeutic intervention
Glucose Hypoglycemia Hyperglycemia	$\leq 3.9 \text{ mmol/L}$ and $< \text{LLN}$ and baseline $> 3.9 \text{ mmol/L}$ or $\geq \text{LLN}$ $\geq 11.1 \text{ mmol/L}$ (unfasted); $\geq 7 \text{ mmol/L}$ (fasted) and baseline $< 11.1 \text{ mmol/L}$ (unfasted); $< 7 \text{ mmol/L}$ (fasted)	
HbA1c	$> 8\%$ and baseline $\leq 8\%$	
Albumin	$\leq 25 \text{ g/L}$ or $\leq \text{LLN}$ (if $\text{LLN} \leq 25 \text{ g/L}$) and baseline $> 25 \text{ g/L}$ or $> \text{LLN}$ (if $\text{LLN} \leq 25 \text{ g/L}$)	
CRP	$> 2 \text{ ULN}$ or $> 10 \text{ mg/L}$ (if ULN not provided) and baseline $\leq 2 \text{ ULN}$ or $\leq 10 \text{ mg/L}$ (if ULN not provided)	
Hematology		

[figure not shown]
[figure not shown]
[figure not shown]
Parameter	PCSV	Comments
WBC	<3.0 Giga/L or <LLN (if LLN ≤3.0 Giga/L) and baseline ≥3.0 Giga/L or ≥LLN (if LLN≤3.0 Giga/L) (Non-Black); <2.0 Giga/L or <LLN (if LLN ≤2.0 Giga/L) and baseline ≥2.0 Giga/L or ≥LLN (if LLN≤2.0 Giga/L) (Black) ≥16.0 Giga/L or ≥ULN (if ULN ≥16.0 Giga/L) and baseline < 16 Giga/L or <ULN (if ULN ≥16.0 Giga/L)	
Lymphocytes	>4.0 Giga/L or >ULN (if ULN ≥4.0 Giga/L) and baseline ≤4.0 Giga/L or ≤ULN (if ULN ≥4.0 Giga/L)	
Neutrophils	<1.5 Giga/L or <LLN (if LLN ≤1.5 Giga/L) and baseline ≥1.5 Giga/L or ≥LLN (if LLN ≤1.5 Giga/L) (Non-Black); <1.0 Giga/L or <LLN (if LLN ≤1.0 Giga/L) and baseline ≥1.0 Giga/L or ≥LLN (if LLN ≤1.0 Giga/L) (Black)	
Monocytes	>0.7 Giga/L or >ULN (if ULN ≥0.7 Giga/L) and baseline ≤0.7 Giga/L or ≤ULN (if ULN ≥0.7 Giga/L)	
Basophils	>0.1 Giga/L or >ULN (if ULN ≥0.1 Giga/L) and baseline ≤0.1 Giga/L or ≤ULN (if ULN ≥0.1 Giga/L)	
Eosinophils	>0.5 Giga/L or >ULN (if ULN ≥0.5 Giga/L) and baseline ≤0.5 Giga/L or ≤ULN (if ULN ≥0.5 Giga/L)	

Parameter	PCSV	Comments
Hemoglobin	
≤ 115 g/L or \leqLLN (if LLN ≤ 115 g/L) and baseline > 115 g/L or $>$LLN (if LLN ≤ 115 g/L) for male; ≤ 95 g/L or \leqLLN (if LLN ≤ 95 g/L) and baseline > 95 g/L or $>$LLN (if LLN ≤ 95 g/L) for Female.
 
≥ 185 g/L or \geqULN (if ULN ≥ 185 g/L) and baseline < 185 g/L or $<$ULN (if ULN ≥ 185 g/L) for Male; ≥ 165 g/L or \geqULN (if ULN ≥ 165 g/L) and baseline < 165 g/L or $<$ULN (if ULN ≥ 165 g/L) for Female
 
Decrease from Baseline ≥ 20 g/L
	Three criteria are independent.
Hematocrit	
≤ 0.37 v/v or \leqLLN (if LLN ≤ 0.37 v/v) and baseline > 0.37 v/v or $>$LLN (if LLN ≤ 0.37 v/v) for Male; ≤ 0.32 v/v or \leqLLN (if LLN ≤ 0.32 v/v) and baseline > 0.32 v/v or $>$LLN (if LLN ≤ 0.32 v/v) for Female
 
≥ 0.55 v/v or \geqULN (if ULN ≥ 0.55 v/v) and baseline < 0.55 v/v or $<$ULN (if ULN ≥ 0.55 v/v) for Male; ≥ 0.5 v/v or \geqULN (if ULN ≥ 0.5 v/v) and baseline < 0.5 v/v or $<$ULN (if ULN ≥ 0.5 v/v) for Female
	Two Criteria are independent
RBC	≥ 6 Tera/L or \geq ULN (if ULN ≥ 6 Tera/L) and baseline < 6 Tera/L or $<$ ULN (if ULN ≥ 6 Tera/L)	
Platelets	
< 100 Giga/L or $<$LLN (if LLN ≤ 100 Giga/L) and baseline ≥ 100 Giga/L or \geqLLN (if LLN ≤ 100 Giga/L)
 
≥ 700 Giga/L or \geqULN (if ULN ≥ 700 Giga/L) and baseline < 700 Giga/L or $<$ULN (if ULN ≥ 700 Giga/L)
	Two independent criteria

Parameter	PCSV	Comments
Vital signs		
HR	<45 bpm and decrease from baseline \geq 20 bpm \geq 120 bpm and increase from baseline \geq 20 bpm	
SBP	\leq 95 mmHg and decrease from baseline \geq 20 mmHg \geq 160 mmHg and increase from baseline \geq 20 mmHg	
DBP	\leq 45 mmHg and decrease from baseline \geq 10 mmHg \geq 110 mmHg and increase from baseline \geq 10 mmHg	

Footnote: Only data collected in this study will be applied to these criteria.

Signature Page for VV-RIM-00192515 v1.0

Approval/eSignature	 2022 13:11:23 GMT+0000
Approval/eSignature	 00
Approval/eSignature	 22 15:42:27 GMT+0000
Approval/eSignature	 22 19:51:37 GMT+0000
Approval/eSignature	 00

Signature Page for VV-RIM-00192515 v1.0 Approved

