7.2. Study Population

7.2.1. Inclusion Criteria

Subjects must meet the following criteria to be eligible for inclusion in the study:

1. Is <12 years of age and ≥ 3 kg to <40 kg at the time parental/guardian consent is signed
2. Has at least one risk factor for developing severe COVID-19 if they were to become infected, such as:
 - a. Obesity (BMI [kg/m^2]) $\geq 95^{\text{th}}$ percentile for age and sex based on CDC growth charts)
 - b. Cardiovascular disease
 - c. Chronic lung disease
 - d. Type 1 or type 2 diabetes mellitus
 - e. Chronic kidney disease, including those on dialysis
 - f. Chronic liver disease
 - g. Immunocompromised or immunodeficient, based on Investigator's assessment (examples include cancer treatment, bone marrow or organ transplantation, immune deficiencies, HIV infection, sickle cell anemia, thalassemia, and prolonged use of immune-weakening medications)

- h. Medical complexities (examples include any underlying genetic condition, neurologic condition, metabolic condition, or congenital heart disease)
- i. **Any other condition** deemed by the Investigator to be a risk factor for severe COVID-19

- 3. Is willing and able to comply with clinic visits and study-related procedures
- 4. Has provided informed consent signed by subject or legally acceptable representative

Note: Age-appropriate assent will be collected from the study subject according to local regulatory (competent authority/ethics) guidelines.

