2.2. Sample Size and Power Considerations

There are no formal hypotheses in this study. The sample size was chosen based on PK considerations and is consistent with early phase studies to assess PK.

At least 12 participants are needed to enroll in each weight group (Group A: ≥ 10 kg to < 40 kg, and Group B: ≥ 3 kg to < 10 kg) to assess drug concentration. The study plans to enroll approximately 28 participants in total.

The sample size may be adjusted if planned SC dosing of casirivimab+imdevimab does not achieve concentrations in serum similar to, or higher than, that observed in adults (≥ 18 years of age) after casirivimab+imdevimab 1200 mg (600 mg per mAb) SC administration. PK will be evaluated on an ongoing basis to determine if dose adjustments are needed and whether more participants are needed for analysis.

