5.8.3. Clinical Laboratory Measurements

Individual participant laboratory parameter measurements will be evaluated by PCSV criteria (See [Appendix 10.1](#)), specifically identifying participants with at least one post-baseline measurement that meets the PCSV criteria. These laboratory parameters will be presented by the biological functions (e.g. red blood cells and platelets, white blood cells, and liver function, etc.). The incidence of PCSVs at any time including data from unscheduled visits during the study period will be summarized.

Listings of laboratory measurements at all timepoints for the participants that meet PCSV criteria will be provided. Listings of all local laboratory measurements will also be provided.

A listing of all women of childbearing potential with a confirmed serum pregnancy test during the study will be provided.

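### The renal flags in SAP 10.1 are adult criteria: a Cockcroft clearance flag would depend on body weight, the creatinine limit is labelled for adults, and the 30% change has no direction

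*SAP*

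**What the plan says.** SAP 5.8.3 evaluates laboratory values against the PCSV criteria in Appendix 10.1. A participant counts if any post-baseline value qualifies: "The incidence of PCSVs at any time including data from unscheduled visits during the study period will be summarized". Laboratory values are also listed.

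Appendix 10.1 has two renal rows.

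- **Creatinine.** There are three independent criteria: an absolute limit of 150 µmol/L, labelled for adults (or the ULN where that is higher); at least "30% change from baseline"; and at least a 100% change. Neither change criterion has a direction. The hemoglobin change criterion and the heart rate and blood pressure rows do state one.
- **Clearance.** The row is headed "Creatinine Clearance (Cockcroft's formula" and has four bands in ml/min: under 15, 15 to under 30, 30 to under 60, and 60 to under 90. They are named end stage, severe, moderate and mild impairment. Each band also requires a baseline at or above its upper limit. The lowest, for example, needs a baseline of at least "15 ml/min (end stage renal impairment". No normalisation for body size is given.

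Where baseline is missing, the appendix drops the baseline half of a criterion. A footnote limits the table: "Only data collected in this study will be applied to these criteria". Serum creatinine is on the laboratory lists (SAP 4.6.3, Protocol 9.2.5); creatinine clearance is not. Under Protocol 7.2.1 participants are under 12 years old and weigh at least 3 kg and less than "40 kg at the time parental/guardian consent is signed". Weight is scheduled only at screening and pre-dose (Protocol Table 3 and 9.2.1).

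**The concern.** The Cockcroft formula multiplies by body weight, so in a small child an absolute clearance in ml/min mainly reflects size. Setting it against fixed stages of impairment makes the label depend on what the child weighs. The creatinine row has two problems of its own: an absolute limit written for adults, and a relative change whose sign is left to the programmer.

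The stakes are in how renal safety is summarised. PCSV incidence is the laboratory summary that SAP 5.8.3 specifies. Children with chronic kidney disease, including those on dialysis, are eligible (Protocol 7.2.1). Group B (3 to under 10 kg) is planned at 12 or more children, so one size-driven label of severe impairment would appear as 1/12 = 8.3%. New enrolment was paused on 28 December 2021 (SAP 1), so the denominator may be smaller.

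**Working it through.** The plan has no figure to reproduce: "There are no formal hypotheses in this study", and the sample size is not formula-based. The check applies the appendix criteria to example children.

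**Inputs.** Bands, baseline conditions and the weight range are from the documents. The SAP names the Cockcroft formula without printing it, so the standard male form is an assumption: clearance = (140 − age) × weight / (72 × creatinine in mg/dL), multiplied by 0.85 for girls. The documents give no creatinine values, so 0.2 to 0.4 mg/dL is illustrative. Example ages are also assumed.

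**1. Same rise, different labels.** Creatinine goes from 0.2 to 0.3 mg/dL (+50%) in boys. Dividing by 72 × 0.2 = 14.4 and 72 × 0.3 = 21.6:

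| Weight, age | (140 − age) × weight | Before | After | Clearance flag |
|---|---|---|---|---|
| 3 kg, 0 y | 420 | 29.2 | 19.4 | none |
| 4 kg, 0.2 y | 559.2 | 38.8 | 25.9 | severe |
| 5 kg, 0.25 y | 698.75 | 48.5 | 32.3 | none |
| 7 kg, 0.7 y | 975.1 | 67.7 | 45.1 | moderate |
| 30 kg, 9 y | 3930 | 272.9 | 181.9 | none |

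**2. Rise needed for the first clearance flag.** With weight fixed at its baseline value and age nearly constant, clearance moves only as the inverse of creatinine. The required rise from 0.2 mg/dL is therefore baseline clearance divided by the next cut-off, minus 1:

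- 3 kg: 29.17/15 = 1.94, a rise above 94%
- 4 kg: 38.83/30 = 1.29, above 29%
- 5 kg: 48.52/30 = 1.62, above 62%
- 7 kg: 67.72/60 = 1.13, above 13%
- 30 kg: 272.9/90 = 3.03, above 203%

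The 3 kg infant starts below 30, so the mild, moderate and severe criteria (baselines of at least 90, 60 and 30) can never be met. Only the end-stage criterion remains.

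**3. No change in creatinine.** With baseline present, an unchanged value stays in its band and the baseline condition fails, so there is no flag at any weight. With baseline missing, a value of 0.3 mg/dL gives 19.4 at 3 kg (severe), 32.3 at 5 kg (moderate) and 181.9 at 30 kg (none). That difference comes almost entirely from weight.

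**4. The adult limit.** 150 µmol/L divided by 88.4 is 1.70 mg/dL, which is 5.7 times a value of 0.3 and 8.5 times a value of 0.2. With a baseline, the 30% and 100% criteria are met long before this limit. Without one, neither change can be computed and this limit is all that remains of the creatinine row.

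**5. Direction.** A move from 0.3 to 0.2 mg/dL is −33%. It is flagged if the change is taken as unsigned, and not flagged if it is (post − baseline)/baseline ≥ 30%. The 100% criterion can be met only by a rise. To size the ambiguity, assume no true change, one post-baseline value per child, and lognormal within-subject variation. The SD of the log ratio is then √(2 ln(1 + CV²)), and flags arise beyond ln 1.3 and, if unsigned, below ln 0.7:

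| Assumed CV | Increase only | Unsigned | Expected of 28, increase only vs unsigned |
|---|---|---|---|
| 10% | 3.2% | 3.7% | 0.9 vs 1.0 |
| 15% | 10.7% | 15.2% | 3.0 vs 4.3 |
| 20% | 17.4% | 27.6% | 4.9 vs 7.7 |
| 25% | 22.6% | 37.8% | 6.3 vs 10.6 |

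**The case against.** The strongest reply is that the clearance row may never be used. The appendix looks generic: it also carries alkaline phosphatase, CPK, uric acid, lipids, HbA1c and CRP, none of which is on the laboratory lists, and the footnote trims it to collected data. Clearance is not a listed variable, and no post-baseline weight is scheduled. This stands as far as it goes: use of the row is not established. But clearance is derived rather than measured, and creatinine, age, sex and baseline weight are all collected, so the footnote does not clearly exclude it.

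A reader might infer that infants with stable renal function would be reported as impaired. The documents do not support that. The baseline condition excludes children already in a band, so a flag needs a recorded boundary crossing or a missing baseline. Protocol 9.1.1 requires the baseline sample before dosing, although it gives PK-ADA samples priority when blood is limited.

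A reader might also infer that a 30% fall will be flagged like a rise. That is one reading; a signed percent change is equally available. The silence still matters because other rows state a direction.

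Finally, it could be said that these flags are the whole renal result and could conceal a real rise. That goes too far. The creatinine criteria operate independently and would pick up the 50% rises above. All local laboratory values are listed, and Protocol 11.4.3.2 plans summaries of change from baseline. The masking in step 2 is confined to the clearance row.

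**Conclusion.** The point holds in limited form. The two renal rows are adult criteria applied to children of 3 to under 40 kg. If clearance is derived, its flags depend on weight: the rise needed from 0.2 mg/dL ranges from 13% at 7 kg to 203% at 30 kg, with 94% at 3 kg. The adult creatinine limit is insensitive at low pediatric values. The 30% criterion is ambiguous, and over assumed CVs of 10% to 25% the unsigned reading adds about 0.2 to 4.3 expected flags among 28 children with no true change.

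These sizes rest on the standard Cockcroft form, illustrative creatinine values and ages, and assumed within-subject variation, none of which the documents give. The effect is confined to the descriptive laboratory safety summary. The primary PK endpoint is untouched. The rows should be corrected before database lock, but they do not threaten the study's main conclusions.

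**What to change.** In SAP Appendix 10.1:

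1. Delete the Cockcroft row. If a clearance measure is wanted, name a size-normalised pediatric eGFR that uses the collected height.
2. Write the two creatinine change criteria as increases from baseline of at least 30% and at least 100%.
3. Replace the adult 150 µmol/L limit with the local age-specific ULN, as a separate criterion.
4. Do not add an above-ULN condition to the 30% criterion. It would suppress real rises that stay within the normal range.

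The cost is an appendix edit and reprogramming of the affected derivations, with no new study assessments. Local age-specific ULNs must be available. If an eGFR is chosen, screening height has to stand in for later visits, because height is scheduled only then. Deleting the row avoids that compromise.

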10.1.3. Events that Require Expedited Reporting to Sponsor

The following events also require reporting to the Sponsor (or designee) within 24 hours of learning of the event:

SAEs.

Adverse Events of Special Interest (AESI):

- Grade ≥ 3 injection-site reactions
- Grade ≥ 3 hypersensitivity reactions

Note: refer to [Table 4](#) for grading scale.

- Multisystem inflammatory syndrome in children (MIS-C)

Note: MIS-C is defined according to the CDC ([CDC, 2021c](#)). All of the following criteria must be met to qualify:

- *An individual aged <21 years presenting with fever ($\geq 38.0^{\circ}\text{C}$ for ≥ 24 hours, or report of subjective fever lasting ≥ 24 hours)*
- *Laboratory evidence of inflammation, including, but not limited to, one or more of the following: an elevated C-reactive protein (CRP), erythrocyte sedimentation rate (ESR), fibrinogen, procalcitonin, d-dimer, ferritin, lactic acid dehydrogenase (LDH), or interleukin 6 (IL-6), elevated neutrophils, reduced lymphocytes and low albumin*
- *Evidence of clinically severe illness requiring hospitalization, with multisystem (≥ 2) organ involvement (cardiac, renal, respiratory, hematologic, gastrointestinal, dermatologic or neurological)*
- *No alternative plausible diagnoses*
- *Positive for current or recent SARS-CoV-2 infection by RT-PCR, serology, or antigen test; or COVID-19 exposure within the 4 weeks prior to the onset of symptoms*

Pregnancy: Although pregnancy is not considered an AE, it is the responsibility of the Investigator to report to the Sponsor (or designee), within 24 hours of identification, any pregnancy occurring in a study participants, during the study or within 8 months of the last dose of study drug. Any complication of pregnancy affecting a female subject, and/or fetus and/or newborn that meets the SAE criteria, must be reported as an SAE. Outcome for all pregnancies should be reported to the Sponsor.

A pregnancy report form will be completed for each subject who becomes pregnant or is pregnant at the time the parent or guardian signs consent.

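### The PCSV table has no low-lymphocyte and no high-neutrophil criterion, so either change goes uncounted when total WBC stays within its limits

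*SAP*

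**What the plan says.** SAP 5.8.3 evaluates laboratory values against the PCSV criteria in Appendix 10.1, "specifically identifying participants with at least one post-baseline measurement that meets the PCSV criteria". It then states: "The incidence of PCSVs at any time including data from unscheduled visits during the study period will be summarized". It adds listings for participants who meet a criterion, and "Listings of all local laboratory measurements will also be provided". It names no other laboratory table.

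In Appendix 10.1:
- The lymphocyte row has an upper limit only: ">4.0 Giga/L or >ULN (if ULN ≥4.0 Giga/L) and baseline ≤4.0 Giga/L".
- The neutrophil row has a lower limit only: "<1.5 Giga/L or <LLN (if LLN ≤1.5 Giga/L) and baseline ≥1.5 Giga/L" for non-Black participants, with 1.0 Giga/L in place of 1.5 for Black participants.
- The WBC row has both sides: a low limit of 3.0 Giga/L (2.0 for Black participants) and a high limit, "≥16.0 Giga/L or ≥ULN (if ULN ≥16.0 Giga/L) and baseline < 16 Giga/L".

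Protocol 10.1.3 defines MIS-C and gives a non-exhaustive list of laboratory evidence, of which one or more is needed. That list ends with "elevated neutrophils, reduced lymphocytes and low albumin". Protocol 11.4.3.2 plans baseline and change-from-baseline summaries of laboratory tests, PCSV counts for each clinical laboratory test, and optional shift tables.

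**The concern.** A one-sided row is not an error in itself. Monocytes, basophils, eosinophils and red cells are tested only when high, and albumin only when low. The question is whether the side chosen is the one of interest in this trial.

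Of the laboratory markers that Protocol 10.1.3 lists for MIS-C, three are on the routine panel (Protocol 9.2.5, SAP 4.6.3): neutrophils, lymphocytes and albumin. Albumin has a PCSV criterion in the direction the protocol names. The other two have criteria only in the opposite direction. Protocol 7.2.1 also admits immunocompromised children, including those on cancer treatment or after transplantation, so low lymphocyte counts are a natural thing to tabulate.

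What is at stake is the laboratory safety tabulation. SAP 5.8.3 makes PCSV incidence its only count of children with abnormal values, and that count expressly includes unscheduled visits.

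**Working it through.** There is no sample-size or power figure to reproduce. The check applies the printed rows to example blood counts.

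**Rules, from SAP Appendix 10.1** (Giga/L, non-Black limits; a local reference limit replaces the fixed one only when it is more extreme):
- Lymphocytes (L): flag if L > max(4.0, ULN) and baseline is not already above that limit.
- Neutrophils (N): flag if N < min(1.5, LLN) and baseline is not already below that limit.
- WBC: flag if WBC < min(3.0, LLN) or WBC ≥ max(16.0, ULN), each with the matching baseline condition.
- Monocytes > 0.7, eosinophils > 0.5, basophils > 0.1, or above the ULN where that is higher.

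**Direction.** From the first rule, no L ≤ 4.0 can be flagged by the lymphocyte row. From the second, no N ≥ 1.5 can be flagged by the neutrophil row. A grid of post-dose and baseline values in steps of 0.1 found no exception. Reading the printed alternatives literally, without substituting the local limit, does not change the direction of either row.

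**Example counts.** These are assumptions, not trial data. Baseline counts are taken as normal (WBC 8.0, N 3.8, L 3.5 in cases 4 to 9), with no local ULN above the fixed upper limits or LLN below the fixed lower limits.

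| Case | WBC | N | L | Flags |
|---|---|---|---|---|
| 1 | 12.0 | 10.8 | 0.5 | none |
| 2 | 15.9 | 15.2 | 0.0 | none |
| 3 | 3.2 | 2.9 | 0.1 | none |
| 4 | 13.0 | 12.0 | 0.5 | none |
| 5 | 8.0 | 7.0 | 0.3 | none |
| 6 | 20.0 | 18.0 | 1.5 | WBC high |
| 7 | 2.5 | 1.8 | 0.4 | WBC low |
| 8 | 10.0 | 3.5 | 6.0 | lymphocytes high |
| 9 | 5.0 | 0.8 | 3.5 | neutrophils low |

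Cases 1 to 3 were run through all six white-cell rows, and cases 4 to 9 through the WBC, lymphocyte and neutrophil rows. In case 1 the other cells are monocytes 0.5, eosinophils 0.1 and basophils 0.1: 10.8 + 0.5 + 0.5 + 0.1 + 0.1 = 12.0. None of these three exceeds its limit.

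**How far the WBC row helps.**
- Neutrophils are part of WBC, so N ≥ 16 implies WBC ≥ 16. With baseline WBC < 16 and a WBC ULN no higher than 16, that is always flagged. Case 6 is flagged even with a WBC ULN of 17.5.
- Below that, N can rise to just under 16.0 minus the other cells. With L = 0.0 and the other cells totalling 0.7 (case 2), the bound is 16.0 − 0.7 = 15.3, so N = 15.2 is not flagged.
- Lymphocytes can fall to zero without a flag as long as WBC stays at or above 3.0 (2.0 in Black participants). A fall in lymphocytes and a rise in neutrophils offset each other in the total.

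**The case against.** The strongest reply is that the PCSV table is not the whole laboratory plan. SAP 4.6.3 says the listed tests, including both counts, will be summarized, and SAP 5 gives minimum and maximum among the default statistics. Protocol 11.4.3.2 plans change-from-baseline summaries, SAP 1.2.3 declares only the neutralizing-antibody analysis dropped, and SAP 6.5 still sets a rule for by-visit summaries. All local values are listed. Medically relevant abnormalities become adverse events (Protocol 10.1.1, SAP 4.6.1). The study is descriptive and planned for about 28 children, so each value can be read individually.

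Much of this stands, and it rules out three stronger readings that a reader might infer:
- *That lymphopenia and neutrophilia can never appear in the safety report.* The routes above, and the WBC row in cases 6 and 7, show otherwise.
- *That cases of MIS-C would be missed.* SAP 4.6.2 records MIS-C by a tick box on the adverse event form, and Protocol 10.1.3 requires it to be reported within 24 hours. No PCSV flag enters that process, and nothing in the documents requires the PCSV table to mirror the MIS-C definition.
- *That the table would show a false zero.* No row for these two directions would be printed at all.

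The reply does not supply a count of affected children. SAP 5.8.3 does not carry the descriptive or shift tables forward. By-visit summaries use scheduled values only (SAP 6.5), so counts drawn at unscheduled visits drop out. A minimum or maximum shows one extreme value but not how many children were affected. Shift tables are optional in the protocol. A listing is not an incidence, and the listing restricted to PCSV participants would omit a child whose only abnormality lies in an untested direction. Adverse event reporting of an isolated laboratory value depends largely on symptoms, treatment or investigator judgment.

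**Conclusion.** The concern holds in a limited form. The PCSV incidence table cannot count low lymphocytes or high neutrophils under their own names, and it cannot register them at all when WBC and the other white-cell rows stay within limits. These are the two cell-count directions that the protocol itself lists as MIS-C laboratory evidence, and SAP 5.8.3 specifies no other count of them.

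The size is minor. No endpoint, hypothesis or decision rule uses PCSV counts, MIS-C ascertainment is unaffected, and individual values remain visible in listings. The direction of the two rows follows from the printed text alone. The examples also rest on assumed counts, on normal baselines and on local reference limits that do not shift the fixed limits. A local WBC ULN above 16 would widen the unflagged range for neutrophils. How many children would be affected cannot be derived from the documents.

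**What to change.** Add two independent criteria to SAP Appendix 10.1 and report them in the same PCSV table:
- a low-lymphocyte criterion, with a condition that baseline did not already meet it;
- a high-neutrophil criterion, with the same kind of baseline condition.

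The appendix's existing rule for a missing baseline can apply to both, and the present rows stay as they are. The sponsor should set age-appropriate thresholds. The local age-specific LLN and ULN are one workable form, but they depart from the neighbouring white-cell rows, which use a fixed limit or a more extreme reference limit, and they would flag marginal excursions.

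It would also help to state in SAP 5.8.3 whether the by-visit and shift summaries of Protocol 11.4.3.2 will be produced. That alone would not replace the criteria: by-visit tables exclude unscheduled values, and the protocol's shift tables are framed as normal or abnormal, without direction.

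The cost is a short SAP revision and two derivations on data already collected, with no new sampling. The downside is a few more mild flags, mainly in children on immunosuppressive treatment.
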